A participating patient might not benefit from participating in this study. However, future patients might benefit from improved lung cancer diagnostics based on these study findings. nCLE combined with EUS has proven to be safe in the field of gastroenterology, lung tumors, and analysis of intrathoracic lymph nodes [10–12]. This minimally invasive imaging technique provides real-time information at a microscopic level about tissues before aspiration. There is little burden related to study participation: before the beginning of the bronchoscopic procedure, fluorescein will be administered intravenously through the existing venous entrance necessary for the sedation. Fluorescein is a standard used dye in hospitals. Adverse reactions are rare (1.1%) and mild in character [13]. According to the literature, in patients without a known allergy to fluorescein, beta-blocker use, or pregnancy, the use of fluorescein is safe. In 2010, Wallace et al. [14] published a retrospective study of all confocal laser endomicroscopy procedures performed between January 2003 and November 2008, or 2,272 procedures (performed under protocol only), and no serious adverse events related to fluorescein injection were identified.

nCLE acquisitions will be performed during Robotic bronchoscopic workup followed by conventional cytological aspirations (routine workup), without aspirations or biopsies for research purposes. The estimated prolonged endoscopy time due to study participation is a maximum of 10 minutes. The patient will not be aware of this as the procedure will be performed under midazolam (fentanyl) or Propofol sedation (following standard practice). Based on previous studies, adverse events are not expected; FNA combined with nCLE is reported to be safe, easy to perform, and a little time-consuming, without adverse events [10,11,15–17]. In conclusion, we believe that the burden and risks associated with study participation are low.

PROTOCOL SIGNATURE PAGE

Needle based confocal laser endomicroscopy for lung cancer diagnosis: A Randomized Controlled Trial

Protocol No.

REVISION 01

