- b. The number and frequency of nCLE procedure-related AE/SAE from the start of the procedure until end of 12-month follow-up
- 8. To assess the reproducibility of nCLE criteria to the reference standard. Three nCLE characteristics for the detection of malignancy were identified during Wijmans et al. study [10]:
 - a. Dark enlarged pleomorphic cells;
 - b. Dark cell clusters consist of overlapping cell structures ('dark clumps') and
 - c. Continuous movement of the cells in one direction ('directional streaming').
- 9. To create an nCLE image atlas for malignant characteristics in PPNs.

3. Study Design

This is a randomized, controlled, interventional, comparative prospective multi-center study. In total, a maximum of 118 consecutive patients with a (suspected) PPN who are referred for a diagnostic bronchoscopic (Robotic-guided TBNA) procedure will be considered for enrollment. The estimated duration of the study is 24 months. Patients will be consecutively recruited and randomly assigned to undergo Robotic-guided TBNA (n=59) or Robotic-nCLE-guided TBNA (n=59).

Only patients in the nCLE arm will receive intravenously administered fluorescein before the start of the Robotic procedure. During the nCLE procedure, an 18G needle enters the targeted tissue, followed by an nCLE AQ-Flex™ 19N Confocal Miniprobe™ (Mauna Kea Technologies, France) through the biopsy needle, to obtain real-time imaging. nCLE imaging will be performed in the PPNs with a total estimated time for research measurements of 10 minutes. nCLE imaging will be performed for each sequential TBNA pass/sampling within the lung nodule lesion and each TBNA path cytopathological result will be correlated with the nCLE sequence acquired for that TBNA pass. TBNA sampling will end when sufficient diagnostic material will be found with ROSE (as assessed by the cytopathologist) or when the physician performing the procedure judges that the number of samplings/passes is adequate. ROSE will be performed by a cytopathologist.

4. Study Population

Population (base)

Patients with a PPN referred for diagnostic bronchoscopic/endosonographic workup tissue sampling based on standard (PET-) CT imaging

Inclusion criteria

To be eligible to participate in this study, a study subject must meet all of the following criteria:

- ≥ 21 years of age
- Suspected PPN
- Nodule size in CT between 8 mm and 30 mm (largest dimension)

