The advantage of nCLE is that it can provide real-time information on a microscopic level of tissues within a solid organ. Therefore, immediate validation of a biopsy location and outcome is possible. Since a needle is used to deliver the optical imaging probes, cell seeding is probably minimal since no tissue is removed by force or taken out of position. For the nCLE procedure, the Confocal Miniprobe™ (AQ-Flex™ 19 N Confocal Miniprobe™, Mauna Kea Technologies, France, was cleared by the FDA for TBNA procedures (K183640)) has been recently designed. This probe is small enough to fit through an 18G aspiration needle, has a resolution of 3.5 μ m, and has a penetration depth of 40-70 μ m.

[figure not shown]

Figure 2: Image (Wijmans/Annema et al. [10]) of EUS guided nCLE in lung cancer patients. nCLE imaging on top with corresponding cytology (lymph node capsule, stroma, vet, vasculature – from left to right)

Summary of known and potential risks and benefits

Fluorescein is a standard used dye in hospitals, where it is used primarily as a contrast dye to visualize the ocular vascular network. In patients without a known allergy to fluorescein, beta-blocker use, or pregnancy, the use of fluorescein is safe. In an extensive prospective review of 11,898 patients undergoing an angiogram with intravenous administration of fluorescein, 132 adverse events were recorded (1.1%) with the most typical reactions being nausea and vomiting [13]. No severe adverse reactions or deaths occurred. Adverse reactions on intravenous administration are rare and primarily mild reactions (Table 1). Fluorescein is widely used in studies with CLE, where it has proved to be safe and easy to perform [10–12].

Table 1. Different types of adverse reactions

Classification	Types of adverse reaction	No. of adverse reactions (%)
Mild	Nausea	87 (0.7)
	Vomiting	47 (0.4)
	Dizziness	34 (0.3)
Moderate	Faint	17 (0.1)
	Localized reactions	14 (0.1)
	Urticaria	28 (0.2)
Severe	Seizure	0 (0.0)
	Myocardial infarction	0 (0.0)
	Anaphylactic attack	0 (0.0)
Death		0 (0.0)

Table 1 Type and number of adverse reactions after intravenous administration of fluorescein in patients undergoing fluorescein angiography (n=11,898). (Kwan et al. 2006)

In 2010, Wallace et al. [14] published a retrospective study of all CLE procedures performed between January 2003 and November 2008, or 2,272 procedures (performed under protocol only), and no serious adverse events related to fluorescein injection were identified.

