Adverse Events (AE) is any unfavorable and unintended sign (including an abnormal laboratory finding), symptom, or disease temporally associated with the use of a medicinal (investigational) product, treatment, or procedure regardless of whether it is considered related to the medical treatment or procedure (NCI CTEP Guidelines March 28, 2011).

Serious Adverse Event (SAE) is an AE that is fatal or life-threatening, requires inpatient hospitalization or prolongation of existing hospitalization (for > 24 hours), persistent or significant incapacity, or substantial disruption of the ability to conduct normal life functions, or is a congenital anomaly. Important medical events that may not result in death but may require hospitalization may be considered an SAE, based upon appropriate medical judgment. A 'life-threatening' adverse event places the patient at immediate risk of death in the judgment of the investigator or sponsor.

Severity Rating

The investigator will evaluate the severity of each adverse event. NCI Common Terminology Criteria for Adverse Events (CTCAE) v.5.0: https://ctep.cancer.gov/protocolDevelopment/electronic_applications/docs/CTCAE_v5.0.xlsx or study

specific toxicity tables provided in the protocol define severity. If not included in CTCAE v.5.0, severity is expressed in numerical grade using the following definitions:

- Grade 1: Mild-asymptomatic or mild symptoms; clinical or diagnostic observations only; intervention not indicated.
- Grade 2: Moderate-minimal, local or noninvasive intervention indicated; limiting age-appropriate instrumental ADL.
- Grade 3: Severe-severe or medically significant but not immediately life-threatening; hospitalization or prolongation of hospitalization indicated; disabling; limiting self-care ADL.
- Grade 4: Life-threatening consequences; urgent intervention indicated.
- Grade 5: Death related to AE

Attribution / Relationship to nCLE or Standard robotic procedure

- Definite – related
- Probable – likely related
- Possible – maybe related
- Unlikely – doubtfully related
- Unrelated – clearly not related

Possible Adverse Events

This is a minimal risk clinical study that poses no additional risk than the standard of care biopsy.

- Hypoxia
- Respiratory failure
- Bleeding at the puncture site
- Pneumothorax
- Infection including pneumonia, bronchitis, or mediastinitis
- Sore throat
- Fever

There is a small risk of allergic reaction to fluorescein:

- Anaphylaxis/hypersensitivity reactions

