All patients will be evaluated for adverse events (AEs) and serious adverse events (SAEs) at the procedure day, 7 days, and 30 days post-procedure. On the day of the procedure the principal investigator will evaluate possible signs and symptoms such as shortness of breath, chest pain, dizziness, low blood oxygen saturation ($\geq 90\%$), hemoptysis (cough bright red blood) and fever ($> 37.3\text{ C}$). At Day 7(post procedure), a study team will contact the patient by the phone and ask about any symptoms of shortness of breath, chest pain, cough with yellow or greenish sputum, hemoptysis (cough bright red blood) and fever. At Day 30, the study team will review patient's medical records and collect data of medications, doctor visits (primary care and specialist visits), procedures and other medical records information. In addition, patients will be instructed to call in with concerns and/or present to the research staff or Principal Investigator. . The study staff will be recording and reporting in the electronic medical record all the adverse events with an attribution of possibly, probably, or definitely related to the study intervention.

Depending on the event, follow up may require additional tests or medical procedures as indicated and/or referral to the general physician or a medical specialist.

Stopping rules based on safety considerations

Investigators will be responsible for data and safety monitoring for this trial. Investigators will discuss with the statistician and/or the study Sponsor if higher than expected rate of adverse events of unacceptable grades are documented. If the rate is more than 10 % of the patient with bleeding, more than 5% with pneumothorax or respiratory failure and 1 patient with anaphylaxis, the principal investigator will consider stopping the study. Statistician and/or Sponsor, after discussion with the Investigator, may recommend to close the study to IRB if the rate of study related adverse events is between the parameters mentioned previously.

6. Data Collection

Subject demographics

- Age
- Sex
- Ethnicity
- Race

Subject medical history and baseline status

- Prior invasive lung procedures and surgeries
- Lung function and diffusing capacity
- Antithrombotic medication current and prior status, including duration of any discontinuation
- Subject risk factors
- Pre-procedure probability of malignancy

Lesion characteristics

- Size
- Location
- Presence of bronchus sign on computerized tomography (CT)

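### The protocol's only numeric oxygen-saturation criterion contradicts its own label, and the adverse-event prompts leave out most of the fluorescein reaction types in Table 1

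*Combined protocol and SAP*

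**What the plan says.** All locations are in section 5 of the combined protocol and SAP unless stated.

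- **Procedure day** (Follow-up of adverse events): the investigator "will evaluate possible signs and symptoms such as shortness of breath, chest pain, dizziness", and the same sentence continues with "low blood oxygen saturation ($\geq 90\%$), hemoptysis" and fever above 37.3 C.
- **Day 7** (same heading): the study team telephones the patient to "ask about any symptoms of shortness of breath, chest pain, cough with yellow or greenish sputum, hemoptysis (cough bright red blood) and fever". Day 30 is a review of medical records.
- **Possible Adverse Events**: hypoxia comes first, with no number attached. For the dye the text says "There is a small risk of allergic reaction to fluorescein", and the only entry beneath is anaphylaxis or hypersensitivity.
- **Summary of known and potential risks and benefits**: in the cited series of 11,898 patients, "132 adverse events were recorded (1.1%) with the most typical reactions being nausea and vomiting". Table 1 gives counts by type.
- **Section 3, Study Design**: "Only patients in the nCLE arm will receive intravenously administered fluorescein before the start of the Robotic procedure".
- **Secondary objective 7**: the number and frequency of all adverse events, and separately of those related to the nCLE procedure, through 12 months.

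**The concern.** There are two separate issues.

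First, a value at or above a cut-off cannot be the definition of a low value. The fever criterion in the same sentence points in the direction of its label, but the saturation criterion does not. Grading and attribution start only after an event has been identified. This check is part of identification, and it holds the only saturation figure in the documents. Sites that read it differently could identify hypoxia differently, and hypoxia counts towards objective 7.

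Second, the prompts do not match the protocol's own account of what fluorescein does. Nausea and vomiting are described as the most typical reactions, yet neither contact prompts for them. The dye is the drug that the study adds, and it is given to one arm only. Mild, short-lived reactions are the kind most likely to go unreported when nobody asks. Because few are expected, one unreported case could decide whether the report shows any at all.

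**Working it through.** **Saturation criterion.** No arithmetic applies. The relevant places, side by side:
- Follow-up of adverse events: labelled *low*, glossed as 90% or above.
- Possible Adverse Events: hypoxia, no number.
- Severity Rating: CTCAE v5.0 or the fallback grades, with no saturation figure in the protocol text.
- Stopping rules: respiratory failure, with no saturation figure.

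The label and the sign cannot both stand, and no other place in the documents settles which was meant. A conversion fault in the symbol cannot be ruled out, so the source file should be checked first.

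**Prompts against Table 1.**

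Reproducing the protocol's rate: 132 / 11,898 = 1.11%, which agrees with the stated 1.1%.

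| Type in Table 1 | Count | Named on procedure day | Named at day 7 |
|---|---|---|---|
| Nausea | 87 | no | no |
| Vomiting | 47 | no | no |
| Dizziness | 34 | yes | no |
| Faint | 17 | no | no |
| Localized reactions | 14 | no | no |
| Urticaria | 28 | no | no |

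Seizure, myocardial infarction, anaphylaxis and death are all zero in the table.

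- Total: 87 + 47 + 34 + 17 + 14 + 28 = 227 reactions.
- Types not named on the procedure day: 227 − 34 = 193, and 193 / 227 = 85%.
- If urticaria is caught by the allergic-reaction monitoring: 193 − 28 = 165, and 165 / 227 = 73%.

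These are shares of reactions, not of patients.

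**Expected numbers in the exposed arm (59 planned).** The text calls the 132 adverse events, but the table sums to 227. The likely explanation is that 132 patients had 227 reactions between them, which is an assumption.
- Expected patients with a reaction: 59 × 132 / 11,898 = 0.65.
- Chance of at least one: 1 − (1 − 132/11,898)^59 = 48%.
- Expected reactions: 59 × 227 / 11,898 = 1.13, of which 59 × 193 / 11,898 = 0.96 are of types not named.

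Range for the assumption:
- If every reaction were in a different patient: 1 − (1 − 227/11,898)^59 = 68%.
- If all reactors were among the 87 with nausea: 1 − (1 − 87/11,898)^59 = 35%.

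On any of these readings, the exposed arm is expected to produce about one reactor or fewer.

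**The case against.** The strongest reply is that neither contact is the only route by which events are collected.

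- The procedure-day list is explicitly illustrative.
- The Definitions text counts any unfavorable sign or symptom as an adverse event, and AEs and SAEs recording and reporting requires all of them on the case report form.
- Section 6 collects adverse events in both the procedural and the follow-up assessments.
- Steps during the procedure requires monitoring for allergic reactions, and patients are told to call in with concerns.

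All of this stands, and it is why under-collection can only be called a risk. It does not remove the mismatch. The day-7 questions are not introduced as examples, and the allergic-reaction monitoring does not mention nausea or vomiting.

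Several stronger readings are tempting but not supported:

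- *Hypoxia will be scored in reverse, or every patient misclassified.* The figure sits in a prompt for signs, severity is graded by CTCAE, and no analysis uses the figure. Staff would have to record a normal reading as low.
- *The respiratory-failure stopping threshold is affected.* That rule uses no saturation value, and respiratory failure is listed separately from hypoxia.
- *Reactions will be missed in the nCLE arm alone, biasing the comparison towards no added risk.* Both arms get the same prompts and are sedated, the documents do not show nausea or dizziness to be specific to the dye, and the allergic-reaction monitoring is described with the dye, which only the nCLE arm receives. The net direction is unknown.
- *Nausea or faint after the dye would be classed as unexpected.* The documents do not name the list of possible adverse events as the reference for expectedness, and Table 1 stands in the same section.
- *The Summary hides moderate reactions by calling them mild.* Section 5 says they are primarily mild and prints the split: (87 + 47 + 34) / 227 = 168 / 227 = 74% mild.

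**Conclusion.** The saturation criterion is wrong as written, because its sign and its label contradict each other and nothing else in the documents resolves the conflict. It should be reconciled before sites use it. This review takes no position on the threshold.

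The prompt gap is a cheap improvement and not an error. Five of the six observed Table 1 reaction types, carrying 85% of reactions (73% if urticaria is caught elsewhere), are not named on the procedure day, and none is named at day 7. The consequence is a possible loss of mild, transient events from objective 7. How many would be lost cannot be estimated from the documents, since the case report form is not included. About 0.65 reactors are expected in 59 patients if the 132 events are patients and if the angiography series carries over to this population and this dosing.

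**What to change.** 1. Check the saturation symbol in the source file. Reconcile the procedure-day criterion with its label and with the hypoxia entry under Possible Adverse Events, with the clinical team confirming the value.
2. Add the Table 1 reaction types as prompts on the procedure-day check, in both arms so that the background rate is measured in the same way. Whether the day-7 call needs any of them is for the sponsor to decide, since the documents give no timing for these reactions.
3. Align the list under Possible Adverse Events with Table 1.

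The cost is protocol and case-report-form wording plus a few tick-boxes at a check already scheduled, with no extra visit. The downside is that more background events, such as nausea after sedation, will be recorded in both arms.

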Per patient diagnostic yield of each bronchoscopic procedure (Robotic-guided TBNA and Robotic-nCLE-guided TBNA) will be calculated, and the accuracy of each technique using the final/definitive diagnosis as the reference. The diagnostic yield and accuracy for each method will be compared.

Patient management:

Three therapeutic management options will be considered right after the Robotic-guided TBNA or Robotic-nCLE-guided TBNA: 'neither treatment nor follow-up', 'follow-up', or 'treatment' (see section 6). If the diagnosis is certain, 'neither surgery nor surveillance' will be recommended for benign nodules; treatment will be recommended for malignant lesions; either treatment or follow-up will be recommended for indeterminate nodules.

Overall diagnostic and therapeutic management proportion differences in the two patient populations (Robotic-guided TBNA arm and Robotic-nCLE-guided TBNA arm) will be compared using a chi-square test. Differences between Robotic-guided TBNA and Robotic-nCLE-guided TBNA arms regarding the specific diagnostic and therapeutic management categories will be compared using McNemar's test.

Safety:

One of the secondary goals of the study is to evaluate the safety of Robotic-nCLE-guided TBNA in comparison to Robotic-guided TBNA. According to the validated Common Terminology Criteria for Adverse Events scale (CTCAE: https://ctep.cancer.gov/protocolDevelopment/electronic_applications/docs/CTCAE_v5.0.xlsx). The primary serious adverse event of concern is treatment-induced pneumothorax. Based on data from a recent sizeable multicentric study [27], Robotic-related Common Terminology Criteria for Adverse Events grade 2 or higher pneumothoraces (requiring admission or chest tube placement) occurred in 2.9%. The Robotic-related Common Terminology Criteria for Adverse Events grade 2 or higher bronchopulmonary hemorrhage and grade 4 or higher respiratory failure rates were 1.5% and 0.7%, respectively. Based on these results, we assume that the pneumothoraces rate among similar patients undergoing Robotic-nCLE-guided TBNA procedures will be equivalent to that study.

9. Study Benefit/Risk Ratio

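### The study-level safety stopping rule cannot be applied as written: its two trigger sentences conflict, and the arm, timing of checks and grade are left open

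*Combined protocol and SAP*

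**What the plan says.** The rule is in Section 5, under Stopping rules based on safety considerations. It has four parts.

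- **Who monitors:** "Investigators will be responsible for data and safety monitoring for this trial".
- **Duty to discuss:** investigators consult the statistician and/or the sponsor "if higher than expected rate of adverse events of unacceptable grades are documented".
- **First trigger:** the bleeding limit comes first, "If the rate is more than 10 % of the patient with bleeding". The same sentence then adds the limits for the other events: "more than 5% with pneumothorax or respiratory failure and 1 patient with anaphylaxis, the principal investigator will consider stopping the study".
- **Closure trigger:** this one lies with the sponsor, the statistician or both, once they have consulted the investigator. They "may recommend to close the study to IRB if the rate of study related adverse events is between the parameters mentioned previously".

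The expected rates are in Section 8, Safety, and come from one cited multicentre study. For pneumothorax, "grade 2 or higher pneumothoraces (requiring admission or chest tube placement) occurred in 2.9" per cent; for the other two events, "hemorrhage and grade 4 or higher respiratory failure rates were 1.5% and 0.7%, respectively", with hemorrhage counted from grade 2. Section 8 expressly carries the pneumothorax rate over to the nCLE arm. It cites the other two rates without that step.

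Sections 3 and 4 give 118 patients randomised 1:1, 59 per arm. Only the nCLE arm receives fluorescein and the probe.

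**The concern.** A stopping rule must let two people looking at the same data agree on whether it has been met. This one does not, for three reasons.

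1. **Joint or alternative.** The first trigger is a list closed by 'and'. It may require a bleeding excess, a pneumothorax or respiratory failure excess and an anaphylaxis together, or it may list separate triggers.
2. **'More than' against 'between'.** The first trigger uses lower limits. The closure trigger asks for a rate between those same figures. Limits of 10% on one event, 5% on another and a count of one on a third do not bound an interval. The event set also changes, from unrestricted events to study-related ones.
3. **Undefined terms.** The rule does not say whether rates are per arm or pooled, or after how many patients they are checked. Grade appears only as unacceptable grades, with no number, whereas the expected rates are grade-specific.

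The chance that the rule is met at rates the protocol itself expects therefore depends on which reading someone adopts during the trial. A pooled rate could also dilute a harm confined to the arm that receives the probe and fluorescein.

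**Working it through.** **Plan's own figure.** The plan gives no operating characteristics for this rule, so there is none to reproduce. The denominators come from the sample size, which does reproduce with the unpooled normal approximation: (1.960 + 0.842)² × (0.7×0.3 + 0.9×0.1) / 0.2² = 58.87, rounded up to 59 per arm and 118 in total.

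**Inputs.**
- Pneumothorax 2.9%, hemorrhage 1.5%, respiratory failure 0.7% (Section 8).
- Pneumothorax or respiratory failure: 2.9% + 0.7% = 3.6%, assuming no patient has both.
- Anaphylaxis: 0 of 11,898 in the fluorescein table of Section 5. Assumed upper value 3/11,898 = 0.025% (rule of three), varied below.
- Event types are treated as independent.

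**Counts that exceed the limits.** More than 5% means at least 6 of 118 (5.1%) or 3 of 59 (5.1%). More than 10% means at least 12 of 118 (10.2%) or 6 of 59 (10.2%).

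**Any-criterion reading, 5% limit alone.** The end look is a binomial tail, P(X ≥ 6 | 118, p) or P(X ≥ 3 | 59, p). Repeated checks use an exact recursion over patients, removing each path at the first n where events/n > 0.05.

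| Check | 118 pooled, 2.9% | 118 pooled, 3.6% | 59 in one arm, 2.9% | 59 in one arm, 3.6% |
|---|---|---|---|---|
| Single end look | 13% | 25% | 24% | 36% |
| After every patient from patient 20 | 41% | 55% | 36% | 48% |
| After every patient from patient 1 | 55% | 66% | 52% | 62% |

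Early looks drive the last row. One event in the first 19 patients already exceeds 5% (1/19 = 5.3%), and at 3.6% that has probability 1 − 0.964¹⁹ = 50%.

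**All-criteria reading, on the same schedule.** With a check after every patient, bleeding (1.5%) and pneumothorax or respiratory failure (3.6%) exceed their limits at the same time in about 4.6% of trials. The chance of at least one anaphylaxis among 59 exposed patients at 3/11,898 is 1 − (1 − 0.000252)⁵⁹ = 1.5%. The product, 0.046 × 0.0148 = 0.0007, is an upper bound of about 0.07%. With an anaphylaxis rate of 0.1% the bound is 0.046 × 0.057 = 0.3%; with 1% it is 0.046 × 0.447 = 2.1%. The anaphylaxis criterion is what makes this reading so rare.

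**The 'between' sentence.** Suppose it means between 5% and 10% for pneumothorax or respiratory failure. Then 6 to 11 events in 118 patients qualify for a closure recommendation and 12 or more do not, so a worse result falls outside the rule.

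**The case against.** Several points on the other side have weight.

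- **The 'and' is probably a list.** Requiring all three excesses together is an unlikely intent. That makes the any-criterion reading the more natural one, but the text does not settle it, and the 'between' sentence fails under either reading.
- **The rule is advisory.** The principal investigator considers stopping and the others may recommend closure. Meeting a limit starts a discussion; it does not end the trial. This stands, and the percentages above are chances of meeting the trigger, not of stopping.
- **There are other safeguards.** The duty to discuss higher-than-expected rates applies however the triggers are read. Serious events go to the sponsor within 24 hours, and investigators report events to their IRB. A procedure can be terminated for a significant complication. A reader might infer that this rule is the only protection, or that the all-criteria reading leaves patients with none. The documents do not support that.
- **'Fires in most trials' needs a schedule that the plan does not state.** A reader might infer it from the 55% and 66%. Those figures assume checks after every patient from the first; a single pooled end look gives 13% and 25%. The plan neither sets nor excludes either schedule, so the range is the finding.
- **Denominator and grade are not wholly absent.** The rule refers to patients and to unacceptable grades, and CTCAE grades are defined in the same section. The terms are under-specified rather than missing.

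The two readings must also be compared on the same schedule. At three times the cited bleeding rate (4.5%), the 10% bleeding limit is crossed in 0.7% of trials at an end look but in 42% with a check after every patient. An end-look figure for one reading should not be set against a running figure for the other.

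**Conclusion.** The point holds as a conflict within the stopping rule, not merely as missing detail. The closure trigger cannot be evaluated from one-sided limits on different events, and taken literally it leaves out the rates above those limits.

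The size depends on the reading. With checks after every patient, the all-criteria reading is met in under 0.1% of trials. The 5% limit alone, as one of several alternatives, is crossed in 55% (2.9%) to 66% (3.6%) of trials pooled over 118 patients, in 41% to 55% if checks begin at patient 20, and in 13% to 25% at one end look.

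These figures assume the cited rates apply to both arms, no overlap between pneumothorax and respiratory failure, independence between event types, and anaphylaxis no more frequent than 3 in 11,898. The cited rates count only grade 2 or higher, or grade 4 or higher, events; if lower grades also count, the any-criterion figures would be larger. Only the pneumothorax rate is expressly assumed for the nCLE arm.

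The primary efficacy analysis is not affected. The sponsor should correct the rule.

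**What to change.** Reconcile the two sentences into one trigger statement that:

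- says whether the criteria are joint or alternative;
- removes or defines the 'between the parameters' condition;
- uses one event set, either all events or study-related events, with the attribution categories that count;
- names the arm or arms, the denominator (for example, patients treated), when checks are made and from which patient, and the CTCAE grade that counts for each event.

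Then report how often the reconciled rule would be met at the Section 8 rates and under the chosen schedule, and at some higher rates that the sponsor would regard as unacceptable. The clinical limits themselves remain the sponsor's decision.

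The cost is protocol wording and a short calculation. Sample size and the primary analysis do not change.
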